9.2 Sample Size and Randomization

The study is powered to detect a clinically meaningful difference between the two intervention groups on the primary outcome (ODI score) at the 12-month follow-up time period. This endpoint was chosen as it represents the durability of the treatment effect and best reflects the potential utility of the FORT-A program for improving the life of patients. The effect sizes used in the calculation are based on our previous FORT trial, for which treatment effects in the FORT study arm were maintained at the one-year follow-up.

Although Aim 2 changed in September 2015, it is important to note that the study must be powered for Aim 1 for two reasons. First, Aim 1 represents the most immediately relevant clinical endpoint, demonstrating that the FORT-A program is clinically superior to Treatment As Usual in this complex patient population. Second, the PI's previous military FORT study revealed a significant decrease in opioid medication use for program completers (compared to TAU). The resulting data suggest that improved pain management through functional restoration is a likely mechanism opioid medication reduction in military pain populations. Thus, Aim 1 must be met to maximize between-groups differences in Aim 2.

To best assess Aim 2, we have chosen to assess medication (opioid and non-opioid) use on a monthly basis (during follow-up assessments and monthly phone calls) using the TLFB and the MQS. The increased frequency in assessment (each measure will be given 12 times) will provide ample power to detect between-groups difference in opioid recidivism over the 12-month study period. Assuming a sample size of $N = 130$ ($n = 65/\text{group}$), 12 data collection periods (monthly follow-ups for one year), and a statistical significance level of 0.05, the analysis will have power = .80 to detect a clinically meaningful difference between the study groups. For example, if the control group exhibits a recidivism rate of 45% (as suggested in Section 2.1 of this document) and the active treatment group exhibits a recidivism rate of 22.5%, the study will have power = .80.

We will enroll $n = 65$ ($N = 130$) and anticipate $\leq 30\%$ all-source attrition rate as in our previous study. Assuming that at the 12-month follow-up the standard care treatment arm will report mean (SD) ODI scores of 19.5 (6.6), using a two-tailed $\alpha = 0.05$, we will have power = 0.80 to detect effect sizes as small as $d = 0.50$. For the ODI, this is equivalent to a clinically meaningful 3.3 point difference between groups. In our original FORT trial, we observed a 9.2 point difference between individuals who were not lost to follow-up at 12-months. Thus, for the intention-to-treat analyses, where we expect that up to 30% of individuals will require imputation of some kind, our expected effect sizes can be attenuated by $\sim 60\%$ with sufficient power to detect a clinically meaningful difference. Differences smaller than 3.3 points on the ODI are unlikely to be clinically meaningful.

Treatment Assignment Procedures

Participants will be randomly assigned to each of the study arms based on the rationale and procedures outlined in sections 6.2.2 and 6.2.3 of this protocol. Masking will be managed using the diagram shown in Figure 2. Pursuant to this diagram, masking will be overseen and maintained through a collaboration between the study coordinator (who will not be blind to any part of this study to all for better tracking of participant flow and AEs; though the Coordinator will not take part in any evaluations and is forbidden to discuss blinded information with any study team member without first discussing it with the PI and the STRONG STAR Administrative Core) and the STRONG STAR Data Core (which maintains the link between identity and participant number). Masking of treatment arm to the participant or provider is absolutely impossible in a behavioral trial. Plans for

retention of the blind are described in sections 5.2, 5.4, and 6.2.3.1 of this protocol. If a blind must be broken (e.g, to protect the safety of a participant), then the blind can only be broken by the study Coordinator and/or Co-Coordinator after consultation and permission from the PI and the STRONG STAR Admin Core. To break the blind, the Coordinator will contact the STRONG STAR Data Core and request revelation of the participant identity and linked unique identifier.

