The few publications describing the effectiveness of the OSI show a significant drop in the rate of opioid prescription in the VA system, especially for veterans on high doses of opioid medications (Westanmo et al., 2015). A PCORI Topic Brief published in June 2015 provides a comprehensive review of the data on safety and efficacy of opioid medications, and the available data largely show that opioid medications are “weakly” effective in the long-term management of chronic pain and there is very little data describing the best way to discontinue opioid medications, and no good research describing the long-term consequences for pain management and opioid recidivism for those who are discontinued (which mirrors Congressional Testimony by VA Official [name] in 2014 describing a large reduction in opioid prescriptions throughout the VA attributable to OSI. The South Texas Veterans Health Care System, where this study will take place, was recently identified as a top ten performer for OSI outcomes, so STVHCS veterans are increasingly likely to become former opioid users.

Although there is little VA data describing the outcome of opioid prescription tapering or discontinuation in veterans, there is some helpful data offering insight into what could occur. A small-scale study of an Opioid Renewal Clinic in the Philadelphia VA found a recidivism rate of over 40% for veterans who discontinued opioids (with higher rates for those not engaged in an intervention program for high risk opioid abusers; Becker et al., 2009). An older study of Vietnam veterans also found a 40% rate of future opioid use after military discharge among veterans who were “addicted” to opioid medication during active duty service (O’Brien et al., 1980). A rat-model study of opiate withdrawal after chronic opioid treatment found an increased rate of cocaine-seeking behaviors (He & Grasing, 2004).

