The FORT program was originally tested in a non-polymorbid active duty military chronic pain sample. The original trial showed that our model of integrated care can effectively improve physical and psychosocial disability among military service members with pain. It has yet to be tested in a polymorbid pain population, but we believe that the CAM-based composition of FORT makes it an excellent substrate for polymorbid pain management. We have expanded on the original FORT trial through several subsequent trials specifically focusing on pain processes in polymorbid military members and Veterans. Data from these subsequent trials have allowed us to tailor the FORT intervention to the specific needs of a polymorbid OEF/OIF/OND Veteran chronic pain population. We have labeled this amended version of the manualized program “FORT-A” (A = Amended), and believe that this new program offers the best available opportunity for polymorbid pain management. The proposed study will recruit 130 OEF/OIF/OND Veterans with polymorbid chronic musculoskeletal pain who are currently using chronic opioid therapy for pain (taking opioid medications daily for 20 out of 30 days a month for three or more months). In 2015, the VA Opioid Safety Initiative (OSI) began to programmatically work toward improving the safety of opioid medication prescription for San Antonio Veterans with chronic pain. As noted above, very little is known about the potential outcomes of this initiative, but the scant available data suggest a rate of opioid recidivism of 30-40% among prior persistent opioid users who get no specialty intervention. To align with this initiative, this study altered the opioid inclusion criterion to include Veterans who were removed from opioid medications during the OSI. These Veterans will be randomly assigned to either the 3-week interdisciplinary FORT-A chronic pain management program (described below) or to

treatment in the South Texas Veterans Health Care System’s (STVHCS) PRC in San Antonio, TX, which represents the best available care for Veterans with deployment-related polymorbid pain. Primary endpoints for this research include pain management (represented in Aim 1) and opioid use (represented in Aim 2) at pre-treatment, post-treatment, 6-month follow-up and 12-month follow-up.

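### The 0.80 power given for Aim 2 in Section 9.2 rests on a control rate and full retention that the rest of the plan does not expect, and it does not demonstrate the benefit claimed for monthly assessment

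*Combined protocol and SAP*

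**What the plan says.** Section 9.2 (Sample Size and Randomization) says that giving each medication measure 12 times "will provide ample power to detect between-groups difference in opioid recidivism over the 12-month study period". It then takes 130 participants, 65 per group, and continues: "12 data collection periods (monthly follow-ups for one year), and a statistical significance level of 0.05, the analysis will have power = .80". The worked example applies "if the control group exhibits a recidivism rate of 45% (as suggested in Section 2.1 of this document") and 22.5% in the active arm. No within-person correlation is given and no loss is deducted.

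Other parts of the plan bear on these inputs:

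- **Control rate.** Section 2.1, the cited source, reports one small VA study that "found a recidivism rate of over 40% for veterans who discontinued opioids" and an older one that "also found a 40% rate of future opioid use after military discharge". Section 2.2 concludes that "the scant available data suggest a rate of opioid recidivism of 30-40% among prior persistent opioid users" without specialty intervention. Section 9.6, Aim 2, repeats 30-40% as the expectation for treatment as usual (TAU).
- **Retention.** The next paragraph of 9.2 anticipates up to 30% "all-source attrition rate as in our previous study". For the intention-to-treat analysis of the Oswestry Disability Index (ODI), it speaks of a setting "where we expect that up to 30% of individuals will require imputation of some kind".
- **Time frame.** Hypothesis 3 in Section 1.1 and the secondary hypothesis in 9.1 refer to 12 months or one year. Section 9.6 compares the arms monthly and defines recidivism over the 30 days before each assessment.
- **Interpretation.** The Aim 2 paragraph of 9.6 reads a significant main effect as differential change in disability.

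**The concern.** A reader who takes 0.80 at face value will treat Aim 2 as adequately powered under the plan's own expectations, helped by 12 assessments. None of that is shown. The rate is above the range used elsewhere, everyone is assumed to be analysed, and the stated figure is what one comparison per person already gives.

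Two things are at stake. First, a null Aim 2 result could be presented as coming from a well-powered comparison when, for status at 12 months, it may not be. Second, status at 12 months and monthly recidivism over follow-up are different quantities. They can give different answers from the same data, and they have different power. The plan should say which one the hypothesis is about.

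**Working it through.** **Inputs.** From 9.2: 65 per arm, 45% against 22.5%, alpha 0.05, 12 occasions, up to 30% attrition. From 2.2 and 9.6: control rate 30-40%. Two-sided testing is stated for the ODI and assumed here for Aim 2.

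**Formula.** For two proportions with n per arm, difference d = p1 − p2 and mean p̄ = (p1 + p2)/2:

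power = Φ{[d − 1.96·√(2p̄(1−p̄)/n)] / √[(p1(1−p1) + p2(1−p2))/n]}

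**Step 1: the plan's own figure.** p1 = 0.45, p2 = 0.225, p̄ = 0.3375, n = 65.

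- Critical difference: 1.96·√(2·0.3375·0.6625/65) = 0.1626.
- Standard error: √[(0.2475 + 0.1744)/65] = 0.0806.
- Power: Φ[(0.225 − 0.1626)/0.0806] = Φ(0.775) = 0.78.

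The unpooled version gives 0.80 and exact enumeration of the uncorrected chi-square gives 0.79. The stated figure therefore reproduces with one outcome per person and no loss.

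**Step 2: what the 12 repeats contribute.** Averaging 12 exchangeable measurements with within-person correlation ρ multiplies the variance by (1 + 11ρ)/12, so the effective n is 12n/(1 + 11ρ). With 45% against 22.5% and 65 per arm, power is 0.96 at ρ = 0.5 and 0.90 at ρ = 0.7. To bring it down to 0.80, ρ must be 0.95 (pooled) to 0.99 (unpooled), where repeats add almost nothing.

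**Step 3: the plan's own control rate, one outcome per person.** Full 30% loss leaves 65 × 0.70 = 45.5 per arm. Section 9.2 does not say whether the relative or the absolute effect would carry over to a lower control rate, so both are shown.

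| Control rate | Halving, 65 per arm | Halving, 45.5 per arm | 22.5 points, 65 per arm | 22.5 points, 45.5 per arm |
|---|---|---|---|---|
| 40% | 0.71 | 0.55 | 0.82 | 0.66 |
| 35% | 0.62 | 0.47 | 0.86 | 0.72 |
| 30% | 0.54 | 0.40 | 0.92 | 0.80 |

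Keeping 22.5 points means relative reductions of 22.5/40 = 56%, 22.5/35 = 64% and 22.5/30 = 75%, against 50% in the 9.2 example. At the 9.2 contrast itself, 45.5 per arm gives 0.63.

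**Step 4: all 12 monthly values, halving.** The values of ρ are assumptions; the documents give none.

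| Control rate | ρ = 0.5, no loss | ρ = 0.7, no loss | ρ = 0.5, full 30% loss | ρ = 0.7, full 30% loss |
|---|---|---|---|---|
| 40% | 0.93 | 0.84 | 0.81 | 0.69 |
| 35% | 0.87 | 0.76 | 0.74 | 0.61 |
| 30% | 0.80 | 0.68 | 0.65 | 0.52 |

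At ρ = 0.3 with no loss, the 40% row would be 0.99.

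**The case against.** The case for leaving the text alone has several parts.

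- **The 0.80 is correct for its inputs.** This stands. A reader might infer a miscalculation; there is none.
- **45% is defensible.** It is offered as an example, it is compatible with a rate above 40%, and Section 2.1 adds that rates were higher in those outside an opioid programme, while 4.2 excludes people in such programmes. This stands as far as it goes. But 2.1 does not state 45%, and 2.2 and 9.6 settle on 30-40%.
- **Halving is only one way to carry the effect over.** This stands. With the absolute difference kept and nobody lost, power is above 0.80, so the documents do not support saying that Aim 2 is underpowered.
- **Full loss is too severe.** This stands. Monthly timeline followback interviews, re-contact of lost participants (6.2.5), the one-year prescription review (9.5.2) and imputation would recover information. With 15% full loss (55.25 per arm), the halving gives 0.63/0.55/0.47. Even with no loss it gives 0.54 to 0.71.
- **The 0.80 could already allow for loss.** With 45.5 per arm and 12 repeats, ρ of 0.64 to 0.67 also gives 0.80. But 9.2 names 65 per group and mentions neither loss nor correlation in that calculation.
- **9.2 and 9.6 agree on a monthly analysis.** Largely true, but 1.1 and 9.1 phrase the hypothesis at 12 months. The precis wording about any 30-day period might suggest a cumulative endpoint; it reads more naturally as the definition of the window.
- **The disability sentence is a copy of the Aim 1 text.** Evidently so. A reader might infer that opioid results would be reported as disability results; the surrounding paragraph makes that unlikely. It still needs correcting.

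**Conclusion.** The point holds as an inconsistency of inputs and an incomplete specification. The stated 0.80 uses a control rate above the plan's own 30-40%, counts all 65 per arm despite anticipated attrition, and at that size does not show the advantage claimed for 12 assessments.

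At 30-40%, with one outcome per person and nobody lost, power is 0.54 to 0.71 for a halving and 0.82 to 0.92 for a 22.5-point difference. If 30% gave no usable data, a worst case, these become 0.40 to 0.55 and 0.66 to 0.80. With monthly data the answer is governed by a correlation that the documents do not state. It is tempting to compress this into one range such as 0.40 to 0.93. The documents do not support that: the upper figure needs no loss and a chosen correlation of 0.5, and a lower correlation would exceed it.

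The figures assume two-sided 0.05 and, for repeats, exchangeable correlation with a constant monthly rate and effect. Severity is minor to moderate: Aim 2 is secondary, and the sample size and Aim 1 are unaffected.

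**What to change.** 1. State one Aim 2 estimand in the same terms in 1.1, 9.1, 9.2 and 9.6: either status in the 30 days before the 12-month visit, or monthly recidivism over follow-up.
2. Restate the 9.2 power at a 30-40% control rate and the expected retention. Name the effect scale (relative or absolute) and the loss assumption, with full loss labelled as worst case. If repeats are used, also give the assumed correlation range, the exchangeable structure and the constant monthly effect. Alternatively, give a source for 45% and reconcile it with 2.2 and 9.6.
3. Remove the claim of ample power unless the restated figure supports it.
4. In 9.6, Aim 2, replace the copied sentence with: *A statistically significant group effect will be interpreted as a difference between arms in opioid recidivism.*

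The cost is wording only, with no new data, visits or participants. The stated Aim 2 power may become less favourable, and the monthly option requires the team to commit to a correlation range that the documents do not now contain.

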Based on our previous FORT trial, for which treatment effects in the FORT study arm were maintained at one-year follow-up, it is reasonable to assume that treatment benefits will be maintained after post-treatment and that all post-baseline measures can be averaged for a main effect of treatment. To detect a medium effect with power = 0.80 (based on Cohen’s standardized mean difference $d=0.50$) at $\alpha = 0.05$, we would require $n=50$ in each study arm for a total sample size of $N=100$ for data analysis. Based on our prior FORT research trial and our ongoing VA trials through STRONG STAR, we anticipate less than 30% attrition with a target recruitment goal of $n=65$ in each arm to account for dropouts. Thus the recruitment target for this research is 130 OEF/OIF/OND Veterans with military service-related new onset or exacerbated chronic musculoskeletal pain and persistent opioid use. Both the FORT-A and PRC treatments will be provided on an outpatient basis through the STVHCS PRC (where the PI has several hundred square feet of research space under a VA WOC appointment; see 5.1 and 5.2 in

this document for a more detailed description of the treatment arms). The overall trial will last 5 years (2014-2019). The IRB protocol for this research was approved on July 10, 2014 (see study binder for most current IRB documents and any amendments submitted and approved to the UTHSCSA/VA IRB). Individual participants will be actively enrolled for one year during which time they will:

- Complete pre-treatment assessments
- Undergo a three-week treatment phase
- Complete post-treatment assessment
- Complete 6-month post-treatment follow-up assessments
- Complete 12-month post-treatment follow-up assessments

The following diagram (Figure 2) outlines the administration for this research and the blinding status of individual study personnel/roles:

Figure 2. Study organizational hierarchy

Key:

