6.2.5 Completion/Final Evaluation

List each assessment to be performed at the participant's final visit.

Visit 16 (One-Year Follow-Up)	Psychosocial Assessment Pain Diary FCE Upload Actiwatch Upload MEMS Adverse Events Opioid/Medication Assessment (including CPRS and PAT) MQS STRONG STAR Common Data	± 50 weeks after treatment ± 2 weeks
----------------------------------	---	---

	Elements Exit Interview	
--	----------------------------	--

All participants will be asked to complete all final assessments, regardless of whether or not they complete the study. After completing the intervention, we will maintain monthly telephone contact with all participants to promote adherence to follow-up assessments and to give them an opportunity to report any adverse events they may have experienced since finishing the three-week intervention phase. This monthly contacts will also include monthly administration of the TLFB for pain medication and opioid medications and administration of the MQS. We will also use these monthly calls to identify and troubleshoot any potential problems with the Actiwatch or MEMS Caps.

Participants who were lost to contact at any point before the 12 month follow-up assessment will be contacted to complete the Missing Data Assessment, ODI, TLFB and Concomitant Meds Form. Participants will be mailed a letter explaining why they are being contacted, how long the phone interview will take, and what information we will collect. The letter will also include opt-out information. Within two weeks of the participants receiving this letter, we will contact participants to discuss whether they would like to participate. The Missing Data Assessment is a 4-item measure of global symptom improvement of pain, perception of satisfaction and burdensomeness of study treatments, and reason(s) for discontinuing study participation. This assessment will be used to assess missing data randomness and to categorize participants who discontinued study participation as a way to help impute missing data and improve future studies with these treatments in similar populations.

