3. *Exacerbation of PTSD or Depression Symptoms*: In any study involving the treatment PTSD, there is a chance that emotional distress may temporarily worsen. If this happens, adjunctive treatment will be provided using the ASAP protocol.
4. *Opioid Withdrawal Symptoms*: During the course of this study, some participants may choose to stop taking opioid medications (though this is not mandatory), which is increasingly likely in light of recent federal changes to VA prescription practices and the VA's Opioid Safety Initiative. Those who discontinue persistent opioid use may report adverse symptoms of opioid withdrawal that will be monitored at all individual, group, and assessment appointments. Should these symptoms be identified, [name] and/or [name] will be notified. They will meet with the PI to discuss if these symptoms can be reasonably addressed under the ASAP protocol.

Participants will continue to be followed with their permission if study intervention is discontinued. There will be no modifications to the schedule and duration of continued followup if the participant is referred to the VA system for treatment and stabilization (though we will ask permission for frequent checks with the participant on their status to ensure that they are doing well and recovering). They will still be asked to complete all measures at all remaining follow-up intervals.

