9.6 Data Analyses

Data Analysis: To examine our aims and hypotheses we will utilize the generalized linear model, which allows specification of an appropriate distribution for each outcome that can accommodate continuous outcomes (e.g., normal distribution with identity or log link for self-reported disability) and presence/absence outcomes (e.g., binomial with logit link for probability of daily opioid use). We will not stratify our analyses by PTSD or depression, but will account for these variables in our data analysis. Furthermore, we will attend to the influence of missing data on our analyses, and plan on conducting missing values analysis to inform several sensitivity analyses (e.g., LOCF, multiple imputation, etc.) to ensure an intent-to treat principle is observed. Specifically, we will examine the MAR assumption by examining patterns of missingness conditional on baseline assessments, treatment adherence, or other time-varying predictors. Our RCT has one primary endpoint (Oswestry), so both primary and secondary outcomes will be interpreted at a conventional level of statistical significance, $p < 0.05$. To adhere to NIH policy of examining gender and ethnic subgroup analyses, we will add interaction terms (i.e., treatment group x subgroup) for each of our planned analyses. Each analysis is further detailed below:

AIM 1: Assess the efficacy of the FORT-A Program for improved pain management outcomes in (N=130) polymorbid OEF/OIF/OND PRC Veterans with chronic orthopedic pain using a 1:1 randomized clinical trial comparing FORT-A to standard PRC care. To examine our primary hypothesis, we will compare the self-reported disability scores of the two groups at 12-month follow-up while controlling for baseline scores (i.e., an ANCOVA approach). A statistically significant main effect will be interpreted as the groups exhibiting differential change in regards disability. Secondary analyses will use growth curve modeling (mixed effects hierarchical regression with polynomial change parameters) which will model differences in change trajectory over time between the groups across assessment occasions.

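### Section 9.2's power of 0.80 for a 3.3-point ODI difference holds only with almost no attrition; Section 3 uses a different basis, and the Aim 2 control rate is inconsistent

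*Combined protocol and SAP*

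**What the plan says.** **ODI.** Section 9.2 powers the 12-month ODI comparison. It gives 65 enrolled per arm, two-sided alpha 0.05, a control mean (SD) of 19.5 (6.6) and all-source attrition of at most 30%, and claims "we will have power = 0.80 to detect effect sizes as small as" d = 0.50, or 3.3 points. It adds: "Differences smaller than 3.3 points on the ODI are unlikely to be clinically meaningful". On attrition it says that in the original FORT trial "we observed a 9.2 point difference between individuals who were not lost to follow-up at 12-months", so for the intention-to-treat analysis, "where we expect that up to 30% of individuals will require imputation of some kind", the expected effect could shrink by about 60% and power would still suffice. Section 9.6 makes the primary analysis a comparison "at 12-month follow-up while controlling for baseline scores (i.e., an ANCOVA approach"). No baseline to 12-month correlation is given.

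**Section 3.** The same d, alpha and power are applied to the average of all post-baseline measures: "we would require $n=50$ in each study arm for a total sample size of $N=100$ for data analysis". The 65 per arm is the target after allowing for dropout of under 30%.

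**Aim 2.** Section 9.2 describes power as ample and gives 0.80 for 45% versus 22.5% recidivism at N = 130 with 12 monthly assessments, citing Section 2.1 for the 45%. Section 2.1 reports over 40% in one study (higher for those outside an intervention programme) and 40% in another. Sections 2.2 and 9.6 give 30-40%.

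**The concern.** The power claim and the attrition allowance stand in the same paragraph of Section 9.2, yet the power appears to be computed on everyone enrolled. The 3.3 points matter because the plan treats anything smaller as unlikely to be clinically meaningful.

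These figures justify N = 130. Section 9.4 relies on them in declining interim analyses, and they would shape how a null result is read. A protocol should also not carry two rationales for one sample size, or two control rates for one endpoint.

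**Working it through.** **1. Reproduce the ODI figure.** Inputs from Section 9.2: difference 3.3, SD 6.6, d = 3.3/6.6 = 0.50, two-sided 0.05, 65 per arm. The normal approximation is Φ(d√(n/2) − 1.96) = Φ(0.5 × √32.5 − 1.96) = Φ(0.89) = 0.813. The noncentral t gives 0.808. The t-test needs 63.8 per arm for 0.80, so equal loss above 1 − 63.77/65 = 1.9% takes unadjusted power below it.

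**2. Apply the plan's own losses.** Noncentral t throughout. For ANCOVA, the SD becomes 6.6√(1 − r²) with one degree of freedom lost. The 65 vs 52 row uses Section 9.3's report that about 20% of treatment-as-usual participants, and no FORT completers, were lost in the original trial (65 × 0.8 = 52). The last row is 65 × 0.7 = 45.5.

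| Analysed per arm | Unadjusted power at 3.3 | r needed for 0.80 | Unadjusted power at 3.68 |
|---|---|---|---|
| 65 / 65 | 0.808 | none | 0.88 |
| 65 / 52 | 0.760 | 0.31 | 0.84 |
| 58.5 / 58.5 (10% loss) | 0.765 | 0.29 | 0.85 |
| 52 / 52 (20% loss) | 0.714 | 0.43 | 0.80 |
| 45.5 / 45.5 (30% bound) | 0.655 | 0.54 | 0.75 |

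At the 30% bound the difference detectable with 80% power is 3.9 points unadjusted.

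**3. Test the attenuation statement.** A 60% reduction leaves 9.2 × 0.4 = 3.68 points, the last column above: 0.88 with 65 per arm, 0.75 at the 30% bound. Reaching 3.3 exactly is a reduction of 1 − 3.3/9.2 = 64%, so the statement appears to rest on the same full-enrolment calculation. If instead the effect is diluted only by the 30% lost, 9.2 × 0.7 = 6.44 points, and power at 45.5 per arm exceeds 0.99.

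**4. Section 3.** 65 enrolled leaves 50 only if loss is at most 1 − 50/65 = 23%; at 30% it leaves 45.5. The 50 may be attainable on Section 3's own basis: averaging three post-baseline visits multiplies the SD by √((1 + 2c)/3), where c is the between-visit correlation. At 50 per arm this gives 0.82 for c = 0.6 and 0.79 for c = 0.7. Both values of c are assumptions; the plan states none.

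**5. Aim 2, single comparison.** Pooled two-proportion test, 65 per arm, no continuity correction. For 45% vs 22.5%, Φ[(0.225 − 1.96√(2 × 0.3375 × 0.6625/65)) / √((0.2475 + 0.1744)/65)] = Φ(0.775) = 0.78, close to the stated 0.80. Halving the rate gives 0.71 at 40% vs 20% and 0.54 at 30% vs 15%. Keeping the 22.5-point absolute difference gives 0.82 at 40% vs 17.5%.

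**6. Aim 2, monthly comparison.** Assume exchangeable within-person correlation ρ, so a person with k months contributes k/(1 + (k − 1)ρ), and a loss of 2.5% of each arm per month, reaching 30%. With the rate halved:

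| Control rate | ρ = 0.5 | ρ = 0.7 | ρ = 0.9 | Largest ρ for 0.80 |
|---|---|---|---|---|
| 45% | 0.95 | 0.88 | 0.81 | 0.92 |
| 40% | 0.91 | 0.82 | 0.73 | 0.75 |
| 35% | 0.85 | 0.75 | 0.65 | 0.60 |
| 30% | 0.77 | 0.66 | 0.56 | 0.46 |

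With 40% vs 17.5% the same model gives 0.94 at ρ = 0.6 and 0.84 at ρ = 0.9.

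**The case against.** Both stated powers reproduce, at least approximately, on the enrolled numbers, so a reader who inferred an arithmetic error would be wrong. Several further defences have force.

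- **The analysis is ANCOVA, so unadjusted power is pessimistic.** True. At the 30% bound r = 0.5 gives 0.78 and r = 0.6 gives 0.84. But the plan states no r and does not attribute the 0.80 to covariate adjustment.
- **Intention-to-treat with imputation keeps about 65 per arm and treats attrition as dilution.** This is the plan's own answer, and Section 9.3 defines the population that way. Imputation keeps the nominal count but does not restore the lost information, although multiple imputation may recover some from earlier visits. The complete-case figures above ignore that gain.
- **The 30% is a ceiling.** It is. Section 6.2.5 says "All participants will be asked to complete all final assessments, regardless of whether or not they complete the study", and Section 8 says of those who stop the intervention: "They will still be asked to complete all measures at all remaining follow-up intervals". Actual loss may be well below 30%, so 0.655 is a bound and not a forecast.
- **The expected effect is much larger than 3.3.** If it is near 9.2 points, power is not in doubt. The problem is confined to the claim made at 3.3 points.
- **Section 3's 50 per arm yields only 0.70.** A reader might infer this from an unadjusted single-visit test, but Section 3 averages visits, so that figure does not refute it.
- **45% is compatible with Section 2.1.** It is, since that section says over 40% and higher without a programme. It is not stated there, however, and the conflict with Sections 2.2 and 9.6 remains.

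**Conclusion.** The point stands as an unsupported power statement plus two internal inconsistencies.

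At 3.3 points, 0.80 requires near-complete follow-up or a correlation the plan does not give. Unadjusted power is 0.76 under the earlier trial's loss pattern and 0.655 at the stated upper bound. The 60% attenuation statement reaches only 0.75 at that bound. Section 3's calculation concerns a different outcome from the 12-month primary analysis, and its allowance covers 23% loss, not 30%.

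The documents do not support the stronger readings that the trial is underpowered for its primary outcome or that Aim 2 falls short. The first depends on r, actual loss and the true effect. The second depends on whether the halving or the 22.5-point difference is carried to lower control rates, and on ρ and the dropout pattern. Halving from 40% still reaches 0.80 up to ρ of about 0.75, and keeping the absolute difference does not lower power. What can be said is that the description of Aim 2 power as ample has no shown basis at the rates Section 9.6 expects.

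**What to change.** 1. In Section 9.2, restate for the 12-month ANCOVA after anticipated attrition: power at 3.3 points, the difference detectable with 80% power, and the 60% attenuation statement. Use the baseline to 12-month ODI correlation from the original FORT data. If it is unavailable, give unadjusted figures labelled as such: about 0.76 at 65 vs 52, and about 0.655 with 3.9 points detectable at the 30% bound.
2. Remove Section 3's calculation of 50 per arm on an averaged outcome, or align it with Section 9.2.
3. Reconcile the 45% and 30-40% control rates across Sections 2.1, 2.2, 9.2 and 9.6. Restate Aim 2 power over that range with a stated target difference, within-person correlation and dropout pattern, and drop the description of power as ample if the result does not bear it out.

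The cost is wording and one recalculation from existing data, with no added patients and no change of analysis. The only downside is that the stated power may look less favourable. The latest version is dated September 2019 and recruitment status is not given; if enrolment is complete, the benefit is accurate reporting and not a different design.
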